**IRB 10-04957**

## **A video game to enhance cognitive health in older adults, children, and adolescents**

## “Characterizing the Synergistic Effects of Physical and Cognitive Training on Attention and Working Memory”

June 18 2022

28  
29  
30 **Study Protocol Approved by Ethics Committee**  
31

32 **Recruitment Criteria**  
33

34 1. Males and Females, aged 55-80  
35 2. Inclusion criteria  
36 a. English speaking  
37 b. Normal or corrected to normal vision and hearing  
38 c. Ability to complete cognitive tasks  
39 d. Ability to cooperate and comply with all study procedures  
40 e. General health/physical fitness allowing safe participation with BBT physical components  
41 f. Be within 2 standard deviations (SD) of age-matched controls on all five of the  
42 neuropsychological composite scores.  
43 3. Exclusion criteria  
44 a. Neurological or psychiatric disorders  
45 b. History of stroke  
46 c. Prior head trauma  
47 d. Psychiatric illness  
48 e. Psychotropic medications  
49 f. Hormonal medications  
50 g. Cardiovascular medications  
51 h. Physical or mental conditions that interfere with daily activities  
52 i. Two or more composite scores exceeded 1.5 SDs.

53  
54 **Procedures**  
55

56 1. Screening for general inclusion/exclusion criteria  
57 2. Consenting  
58 3. Baseline outcome data collection  
59 4. Cognitive control training intervention period  
60 5. Return visit to UCSF for post-intervention outcome data collection  
61 6. Return to UCSF for 1-year outcome data collection

62 **Measures administered**  
63

64 1. CPT  
65 2. Working Memory Task  
66 3. Frontal Theta Power  
67 4. Filter Assessment  
68 5. Frontal Theta ITC  
69 6. Diastolic Blood Pressure

70 **Time commitment**  
71

72 • Consenting: 30 minutes based on individual reading speed and comprehension level  
73 • Outcome assessments at baseline, 2-month, and 1 year time points: 2 hours  
74 • Intervention training: 25-35 minutes 3-5x/week for 6-8weeks, depending on intervention arm assigned

The augmentation of deficient attention abilities is especially of interest for older adults, given well-documented age-related declines in these abilities, which are exacerbated in the presence of comorbidity. Over the last decade there has been a surge of research aimed at improving cognitive abilities by harnessing neuroplasticity via cognitive training. Cognitive training as a whole has come under increased scrutiny given consistent shortcomings in study design and outcomes: i) minimal extension of effects beyond the training interventions themselves, ii) lack of appropriate control groups, and iii) absence of follow-up testing to assess sustainability of observed effects. However, there have been several notable examples of cognitive interventions enhancing non-trained cognitive abilities in older adults, with these findings aligning with systematic reviews supporting the utility of cognitive interventions in the older adult population.

In contrast to the uncertainty surrounding the benefits of cognitive training, the utility of physical fitness interventions for older adults' general health has been well established. Fitness-based interventions have also been shown to benefit cognitive control abilities, with such findings hinting at the possibility that combining cognitive and physical training approaches may lead to greater cognitive benefits than either approach alone (although not supported). The use of combined cognitive and physical interventions are especially compelling as a strategy to improve both cognitive and physical health, given that such a pairing can be a time- and resource-effective approach to addressing multiple risk factors in older adults. Indeed, combined training has been shown to result in greater participant enjoyment compared to either sequential training or physical exercise alone. However, while the typical model of alternating between physical and cognitive training has shown to have some cognitive benefits, this resource-intensive tactic requires a multitude of human and material resources. Alternatively, one resource-effective approach in this arena has been the use of exergames; however, it remains unclear how effective such approaches are at improving cognitive and physical outcomes in aging populations, leaving an open question of their overall utility.

We have previously demonstrated that cognitive interventions using closed-loop, adaptive algorithms led to target specific cognitive abilities in older adults can improve task performance and neural measures of cognition, with some evidence of these effects persisting well after the intervention period. These interventions, delivered as engaging video games, have shown positive effects not only with older adults, but in diverse populations, with previous work highlighting the possibility of returning performance on measures of cognitive function to young adult level. Here we created a novel exergame intervention for older adults (Body-Brain Trainer, **figure 1**) that requires participants to perform full-body, physical movements in response to cognitive challenges that engage different cognitive control domains. As in our previous work, we integrated real-time adaptivity and closed loop mechanics for each cognitive ability being challenged. Given the movement demands of BBT, we also

12 implemented an adaptive physical fitness challenge by using real-time heart rate data to titrate game play for a  
13 personalized and integrated training experience across both cognitive and physical domains (see **Methods** and  
14 **Supplementary Materials** for more details on the BBT software).

15 In the present study, we sought to evaluate the primary question of whether BBT could improve measures of  
16 attention and physical fitness in older adults beyond that of an expectancy-matched, active placebo control group. To  
17 the best of our knowledge, this design is noteworthy given that the use of expectancy matching has been absent in all  
18 previous efforts examining cognitive benefits from combined approaches, including those studies designed to evidence  
19 potential synergistic effects through mechanistic control groups (see **Supplemental Materials** for a brief treatise  
20 describing our rationale for utilizing this particular control group). We also interrogated the following secondary  
21 questions: what is the neural mechanism underlying positive cognitive effects, do any observed cognitive improvements  
22 persist one year later without booster training sessions, does BBT result in older adults achieving comparable levels to  
23 young adults on our primary outcome measure, and does this intervention affect other measures of cognitive control  
24 (working memory).

## 25

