Statistical Analysis Approach

IRB 10-04957

A video game to enhance cognitive health in older adults, children, and adolescents

“Characterizing the Synergistic Effects of Physical and Cognitive Training on Attention and Working Memory”

May 31 2023

Statistical Analysis Approach:

Analyses were conducted by researchers who were blind to group membership. To test for training effects on each of the collected outcome measures, we used an repeated measures ANOVA approach as in our previous work^{1,2}. Statistically, no between-group differences assessed using independent t-tests were observed for at baseline involving: (1) age ($t_{47}= 0.35$, $p= 0.73$); (2) gender ($t_{47}= -0.15$, $p= 0.88$); (3) CPT performance ($t_{45}= 1.84$, $p= .07$); (4) Filter task performance ($t_{46}= 1.34$, $p= .19$); (5) mft power ($t_{44}= 1.70$, $p= .10$); (6) mft ITC ($t_{41}= 1.11$, $p= .28$); (7) limits of stability ($t_{44}= 1.05$, $p= .30$); (8) diastolic blood pressure ($t_{43}= 1.77$, $p= .08$). For those measures that showed a trend towards a group difference at baseline (CPT performance, mft power, and blood pressure), we performed an analysis of covariance (ANCOVA) with post-training performance as the dependent variable, pre-training performance as the covariate, and group as the fixed factor. Our reasoning for using this approach is that this analysis accounts for variation around the post-test means that arises from the variation where participants began at pretest³. Using this approach, we observed a nearly significant group difference following training for the CPT task ($F_{(1,46)}= 3.85$, $p=0.056$), a significant group effect for mft power ($F_{(1,44)}= 4.35$, $p=0.043$) and a significant group effect for diastolic blood pressure ($F_{(1,42)}= 6.93$, $p=0.012$), supporting the assertion that the reported ANOVA effects were not driven by trending baseline differences between groups. For post-hoc analysis of the within-group changes, we performed two-tailed, paired-sample t-tests on each group separately to test for significant differences between each testing session. We report Cohen's d for all significant ($p< .05$) and trending ($p< .10$) ANOVA results, using the Hedges and Olkin correction⁴ for small sample bias.

References

- 1 Anguera, J. A. *et al.* Video game training enhances cognitive control in older adults. *Nature* **501**, 97-101, doi:nature12486 [pii] 10.1038/nature12486 [doi] (2013).

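### The protocol asks for the neural mechanism of the cognitive gain, but every analysis in the SAP handles theta and CPT separately, so none relates one to the other

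*Protocol*

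**What the plan says.** The protocol's introductory text, just before Methods, moves from the primary question to several secondary ones: "questions: what is the neural mechanism underlying positive cognitive effects, do any observed cognitive improvements" and so on. Under Neural Cognitive Control Assessments, mft power is the chosen marker. It is taken from the vigilance task, which also yields the primary outcome, CPT tau. That section mentions a correlation between theta and response time variability, but as cited background and not as a planned analysis. Under Participants, the EEG measure is among the exploratory outcomes.

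The SAP has three kinds of efficacy analysis:

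- The main method: "To test for training effects on each of the collected outcome measures, we used an repeated measures ANOVA approach as in our previous work".
- For outcomes with a baseline trend (CPT, mft power, diastolic pressure), an ANCOVA with "post-training performance as the dependent variable, pre-training performance as the covariate, and group as the fixed factor".
- Post hoc: "we performed two-tailed, paired-sample t-tests on each group separately to test for significant differences between each testing session".

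The ANCOVA results given are F(1,46)=3.85, p=0.056 for CPT and F(1,44)=4.35, p=0.043 for mft power.

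**The concern.** To ask what mechanism underlies a cognitive gain is to ask whether the neural change and the cognitive change go together in the same people. A model with one outcome in it cannot show that. If theta and CPT each differ by arm, theta may carry the CPT gain, or training may have produced two unrelated effects. The second is plausible here because the arms differ in exercise, trainer contact, setting and screen, as the protocol's Study Design and expectancy sections describe.

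What is at stake is how the secondary question is answered. The plan gives a reader nothing with which to judge a link, although the theta and CPT data come from the same task at the same two sessions.

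**Working it through.** **1. The SAP's own figures.** The upper tail of F(1,46) at 3.85 is 0.0558 (stated 0.056). The upper tail of F(1,44) at 4.35 is 0.0428 (stated 0.043). Both reproduce.

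**2. Which analyses contain both theta and CPT?**

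| SAP analysis | Outcomes in one model | Relates theta change to CPT change? |
|---|---|---|
| Repeated measures ANOVA | one | no |
| ANCOVA | one, with its own baseline | no |
| Paired t-test within arm | one | no |

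**3. Effect sizes implied by the F values.** For nearly equal arms, and ignoring the small effect of covariate imbalance, d ≈ 2√(F/N). Take N as error df + 3, for two groups and one covariate.

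- CPT: 2√(3.85/49) = 0.56 SD
- mft power: 2√(4.35/47) = 0.61 SD

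**4. How often do both arm tests succeed with no link?** If the two changes are independent within arm, the joint probability is the product of the two powers. Each power comes from the noncentral t distribution at two-sided 0.05, with noncentrality d√(n₁n₀/(n₁+n₀)). The documents do not split EEG losses by arm, so two assumed sets of arm sizes are shown.

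| True effect on each outcome (assumed) | 22 vs 24: power, joint | 24 vs 25: power, joint |
|---|---|---|
| 0.5 SD | 0.381, 15% | 0.403, 16% |
| 0.56 SD | 0.459, 21% | 0.484, 23% |
| 0.6 SD | 0.511, 26% | 0.539, 29% |
| 0.8 SD | 0.755, 57% | 0.783, 61% |

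**5. Does the pattern separate linked from unlinked?** In 20,000 simulated trials per setting (22 vs 24), both arm tests were significant this often:

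- at 0.6 SD: 26% with zero within-arm correlation, 34% with a correlation of 0.5
- at 0.8 SD: 57% and 63%

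The two-test pattern hardly moves. An arm-adjusted correlation test on the same data rejects in 5% of trials at zero link, 52-53% at 0.3 and 95% at 0.5.

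**6. How many participants have both measures?** Study Design reports 49 with complete pre and post data. EEG was lost for 3 at pre-training, and time-locking failed for 4 at pre-training and 4 at post-training. That leaves 49 − 3 − 4 = 42 at pre-training. With both sessions it leaves 38 (no overlap) to 42 (full overlap), if all losses fall among the 49. The SAP implies more for mft power: t with 44 df gives 46 at baseline, and F(1,44) gives 47. The CPT counts also differ within the SAP: t with 45 df gives 47, and F(1,46) gives 49.

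**7. Precision of a link estimate.** Fisher interval: tanh(atanh r ± 1.96/√(N−3)), with atanh 0.3 = 0.3095.

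- N=38: 0.3095 ± 0.3313, so an observed r of 0.3 has 95% CI −0.02 to 0.57
- N=46: 0.3095 ± 0.2989, so 0.01 to 0.54

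Adjusting for arm costs one more degree of freedom and changes these by less than 0.01. The r detectable with 80% power, tanh((1.96+0.84)/√(N−3)), is 0.44 at N=38 and 0.40 at N=46.

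**The case against.** The strongest reply is that no harm is written into the plan. A reader might infer that the theta result of p=0.043, set beside a CPT effect, will be presented as the mechanism. Neither document says so. The SAP uses that p-value for one purpose, to argue that baseline imbalance did not produce the ANOVA effects. This stands, and the point is confined to an unanswered question.

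A reader might also infer that the two-test pattern would usually appear with no mechanism present. That needs about 0.8 SD on each outcome. At the effects the F values imply, it appears in roughly a quarter of trials. The CPT ANCOVA, at p=0.056, does not itself complete the pattern.

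Third, the study is presented as a feasibility and early efficacy study with exploratory EEG, and the link test has only 45-53% power at a correlation of 0.3 (N=38 to 46). This lowers the severity and means a null result would say little. It does not supply the missing analysis, because the protocol still lists mechanism among its secondary questions.

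Finally, the Supplementary Materials are not among the documents, so an analysis described only there would not be visible.

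**Conclusion.** The point holds as a gap between a stated question and the planned analyses. The protocol asks for a mechanism, and nothing in the protocol or SAP relates theta change to CPT tau change. That follows from reading the two documents and needs no assumption. The simulated and computed percentages do rest on assumptions: equal effects on the two outcomes, normal data, a two-sided 0.05 level and assumed arm sizes. They only illustrate how little two separate arm tests say about a link.

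It would go too far to conclude that a positive association would establish mechanism. Theta is not randomised, and both measures come from the same task and sessions, so shared state such as fatigue or effort could produce one.

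Severity is low. The EEG measure is exploratory and the primary CPT comparison is untouched.

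**What to change.** 1. Reconcile the number of participants with usable EEG at both sessions between the protocol's Study Design and the SAP's degrees of freedom, and state it by arm.
2. Add one analysis to the SAP, labelled exploratory and post hoc because results are already reported there. Regress post-training CPT tau on pre-training tau, arm, pre-training mft power and pre-to-post mft power change. Pre-training mft power belongs in the model because the SAP reports a baseline trend for it (p=.10). Report the coefficient for mft change and an arm-adjusted change-change correlation, both with 95% CIs.
3. Reword the secondary question and any conclusion to 'neural correlate', or ask whether BBT changes midline frontal theta. Do this whatever the association turns out to be.
4. State that an arm effect on theta alone is not evidence of mechanism.

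The cost is one regression on data already collected and a few changed words. The downside is a weaker claim with a wide interval.

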## 26 METHODS

### 27 Participants:

28 The study was approved by the Committee on Human Research at the University of California, San Francisco, and  
29 retrospectively registered on ISRCTN registry [ISRCTN [66423499] to distinguish the goals and approach taken here from  
30 those of the 'parent' registration (clinicaltrials.gov submission NCT03032796). This study was designed to gauge the  
31 feasibility and potential efficacy of using the BBT intervention compared to an expectancy matched active placebo  
32 group, for a subsequent mechanistic trial exploring synergistic effects of a combined intervention versus individual  
33 components alone (as described in the 'parent' clinicaltrials.gov submission). For continuity and cohesion, we used the  
34 same primary (CPT) and secondary (Working Memory Task) outcome measures listed in the parent clinicaltrials.gov  
35 registration. Furthermore, here we also examined a subset of the exploratory outcomes listed in the parent registration  
36 (blood pressure, event-related spectral perturbation derived from EEG) as well as two new exploratory measures (Filter  
37 Task, Limit of Stability Assessment). 49 healthy, older adult (OA) individuals consented to participate in this study. OAs  
38 were randomly assigned (block size of 5) to a training group (body-brain trainer; BBT; N=24, mean age=68.8 +/- 5.9, 13  
39 females) or an active, expectancy-matched control group (mind-body trainer; MBT; N=25, mean age=68.20 +/- 6.75, 13  
40 females). All participants were from the San Francisco Bay Area and recruited through online and newspaper  
41 advertisements. All participants had normal or corrected-to-normal vision, had no history of stroke, traumatic brain  
42 injury, or psychiatric illness, were not taking psychotropic, hormonal, or cardiovascular medications, and did not have  
43 any physical or mental conditions that may interfere with their daily activities (e.g., migraine headaches, substance  
44 abuse, neuropathy). Similar to our previous work, all participants reported playing less than 2-hours of video games per  
45 month, and completed a general health questionnaire reviewed by the study team assessing each individual's current

46 state of physical fitness to ensure that they could safely engage with the physical aspects of the BBT platform. All  
47 participants gave written informed consent, and were paid \$15/hour for their in-lab and at-home participation. All  
48 participants were encouraged to not change any aspects of their daily routine (e.g. to change exercise habits) for the  
49 duration of the study.

50

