14 for each theme, and increasing difficulty. For each puzzle, users are given a task (e.g., plant trees according to  
15 specific rules), a time limit, and several hints that they can unlock. Participants were instructed to spend  
16 approximately 10 min with each app each training day (5 days per week for 6 weeks). For Duolingo, the time  
17 was set internally in the app. For the other two apps, participants self-timed their training, and they recorded  
18 their time on a training log. All participants completed the MBT intervention at home using an iPad Mini 2 (iOS  
19 version 8.2; Apple) that was supplied by the UCSF Neuroscape Center. On the day they were given their iPad to  
20 begin training, participants were also provided an instructional binder with instructions on how to play, a  
21 calendar for recording notes and comments throughout their training experience, and were given e-mail support  
22 throughout the intervention period. Throughout the intervention period, technical support for the iPads and all  
23 software was provided via e-mail, phone, and in-person contact, when needed.

24

25 Because these apps were commercial apps and not designed to send data to our server, we took additional  
26 steps to track compliance in the MBT group. On the day they were given their iPad to begin training, participants  
27 were also provided an instructional binder with instructions on how to play, a calendar for recording notes and  
28 comments throughout their training experience, and were given e-mail support throughout the treatment  
29 period. They were instructed to try to split their time equally among the three apps. Upon completion of the  
30 training, researchers confirmed the participants' logged training times.

31

32 **Behavioral Cognitive Control Assessments:**

33 *Attention without distraction.* A custom continuous performance task (CPT) designed in Presentation  
34 (<http://neurobs.com>) was used to assess vigilance without distraction. This tool is a modified version of a well-  
35 validated vigilance task (**Figure 2a**), the Test of Variables of Attention (TOVA), that we have used as an outcome  
36 measure in previous intervention studies. As our metric of interest, we focused on the ex-gaussian tau of  
37 response times, a non-parametric measure of distribution skewing that quantifies attentional lapses by  

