38 examining the distribution of long response times. Several studies have demonstrated a clear advantage of this  
39 measure over traditional measures of response time (although we report on traditional metrics of response  
40 time and response time variance in the **Supplemental Materials**) given that it explains a greater proportion of  
41 variance without needing to employ data trimming techniques. Importantly, this measure has been shown  
42 to reflect performance inconsistencies that are especially present in both healthy older adults and those with

43 mild cognitive impairment, and has been used to support neural noise and dedifferentiation theories  
44 of cognitive aging.

45 For the present study, we adapted the task for use with EEG recordings, which requires many trials with  
46 an actual response, and also facilitates the examination of ex-gaussian tau, a non-parametric measure of  
47 distribution skewing of response times. In this task, participants maintain fixation on a central crosshairs  
48 and grey squares are shown on a black background at the top or bottom of the field of view. Stimuli are  
49 presented frequently at the top of the screen as a 4:1 ratio of targets to nontargets and participants are  
50 instructed to only respond to these stimuli. Participants completed 2 blocks of 125 trials with 100 targets per  
51 block, yielding 200 total targets and 50 non-target trials.

52

53 *Working memory fidelity task.* We used a delayed recognition working memory paradigm designed to measure changes  
54 in participants' ability to maintain an accurate mental representation of items in working memory either in presence or  
55 absence of distracting or interfering information. We have used versions of this task in numerous previous  
56 studies. To summarize briefly, this paradigm consisted of three different conditions that were presented in  
57 blocks: 1) no distraction (ND), 2) Ignore distractor (ID, distractor was present, but participants were informed that the  
58 distractor was to be ignored), and 3) Attend Distractor (AD, participants were required to make a judgment about the  
59 interfering stimulus). Each run was preceded by an instruction slide informing the participant which condition they  

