60 would be performing. Each trial began with the presentation of a face displayed for 800 ms, followed by a delay period  
61 (3 s), the presentation of a face stimulus as a distractor in the ID and AD conditions (800 ms), a second delay period (3 s),  
62 and the presentation of a face probe (1 s). The participants were instructed to make a match/nonmatch button press  
63 response at the probe as quickly as possible, without sacrificing accuracy. This was followed by a self-paced intertrial  
64 interval (ITI). The experiment was programmed in E-Prime (<https://pstnet.com/products/e-prime/>) and the stimuli were  
65 presented on a CRT monitor.

66

67 *Basic response time task.* Here we administered a basic response time (BRT) task as a measure of simple motoric  
68 response time to ensure that any differences observed between groups were not due to differences in basic motoric  
69 quickness. Basic motor speed was assessed in the form of a simple target-detection task during their pre-training  
70 assessment, to ensure that any training-related enhancements in performance were not attributed to a general motoric  
71 speed increase, but rather to enhancements in cognitive control processes. On this task participants pressed a keyboard  
72 button as quickly as possible upon the appearance of a circle at the center of the screen (50 trials). Average response  
73 time (the time between the target appearance and button press) was assayed as a unit of basic motor speed.

74

75 *Complex visual discrimination amid distractions.* For this exploratory measure of attention in the presence of variable  
76 distraction (considered exploratory given that it was not described in the parent clinicaltrial.gov submission), we used a  
77 custom Filter Task (**Supplemental Figure 7a**) to assess how well participants were able to identify targets in the  
78 presence of task-irrelevant information. The experiment was programmed in MATLAB's psychophysics toolbox  
79 (<http://psychtoolbox.org/>) and the stimuli were presented on a CRT monitor. In this task, participants must attend to an  
80 array of different numbers of items (either 1 or 3 red rectangles) with or without the presence of 2 visual distractors (2  
81 blue or green rectangles): set size 1 no distractors (1 total item), set size 1 with distractors (3 total items), set size 3 no  

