82 distractors (3 total items), set size 3 with distractors (5 total items). Half of each of the trials for each condition began  
83 with a cue indicating the participant should attend to either the left or the right side of the screen. The procedure for  
84 each trial began with a 750 ms fixation cross following by a right/left cue (200ms) and then a 300 ms blank ISI. Next, a  
85 sample set from one of the four conditions was shown for 200ms followed by a 900 ms blank delay and then a probe set  
86 containing the same number of red rectangles as in the sample in either the same orientation or with a single rectangle  
87 of altered orientation (50% of each). The probe screen remained visible until participants responded with a "Yes" or  
88 "No" button press indicating whether or not one of the attended rectangles changed orientation. Participants  
89 completed 8 blocks of 80 trials, yielding 160 trials per condition. Participants were instructed to respond as fast as  
90 possible without sacrificing accuracy. As in our previous work, we focused on Response Time Variability (RTV) as our  
91 measure of interest here.

92  
93

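### The Working Memory Task, the only named secondary outcome, has no named score in the documents and no reported baseline comparison or ANCOVA in the SAP

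*Protocol*

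**What the plan says.** **Status of the outcome.** In Methods, Participants, the protocol says the trial used the "same primary (CPT) and secondary (Working Memory Task) outcome measures listed in the parent clinicaltrials.gov" registration. The other outcomes named there are exploratory. The introduction's secondary questions include "young adults on our primary outcome measure, and does this intervention affect other measures of cognitive control", with working memory given in brackets as the measure meant. The list of measures administered has only the entry "Working Memory Task".

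**The score.** The paragraph on the working memory fidelity task sets out its conditions in "blocks: 1) no distraction (ND), 2) Ignore distractor (ID, distractor was present, but participants were informed that the" and so on to a third, attend-distractor (AD). Participants give a match or nonmatch "response at the probe as quickly as possible, without sacrificing accuracy". No score, condition of interest or rule for combining conditions follows. Other tasks are treated differently. For the CPT the protocol writes "As our metric of interest, we focused on the ex-gaussian tau of" response times, for the Filter task it names response time variability, and for the basic response time task it names the average response time.

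**The analysis.** The SAP applies repeated-measures ANOVA to all collected outcomes. It reports eight baseline comparisons: age, gender, CPT, Filter task, mft power, mft ITC, limits of stability and diastolic blood pressure. It continues: "For those measures that showed a trend towards a group difference at baseline (CPT performance, mft power, and blood pressure), we performed" an ANCOVA of the post-training value on the pre-training value and group. Apart from the study title, the SAP does not mention working memory.

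**The concern.** The baseline list takes in exploratory measures, among them the two the protocol calls new (Filter task and limits of stability), but not the one outcome labelled secondary. Since the SAP turns to ANCOVA on the strength of a baseline trend, an outcome with no reported baseline comparison has no visible route to it. The SAP justifies ANCOVA by the need to allow for where participants started, and that reason applies equally to working memory.

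The unnamed score is a second gap. Three conditions and at least two response dimensions leave several possible results for one outcome. The SAP states no multiplicity adjustment and treats p<.10 as trending. At stake is how much weight a reader can give to a working memory result, favourable or not.

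**Working it through.** **1. Reproducing the SAP's figures.** Two-sided p from each stated t and df:

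| Variable | t (df) | Stated p | Recomputed p |
|---|---|---|---|
| Age | 0.35 (47) | .73 | .728 |
| Gender | -0.15 (47) | .88 | .881 |
| CPT | 1.84 (45) | .07 | .072 |
| Filter task | 1.34 (46) | .19 | .187 |
| mft power | 1.70 (44) | .10 | .096 |
| mft ITC | 1.11 (41) | .28 | .274 |
| Limits of stability | 1.05 (44) | .30 | .300 |
| Diastolic BP | 1.77 (43) | .08 | .084 |
| Working memory | none given | none given | not computable |

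The mft ITC difference is within the rounding of t. The ANCOVA p-values also reproduce: CPT .0558 (stated .056), mft power .0428 (.043), diastolic BP .0118 (.012).

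**2. The trigger.** The three measures given ANCOVA are exactly those with recomputed p<.10, so the rule works as a p<.10 rule. For working memory there is no t, df or p, so whether it met the rule cannot be determined.

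**3. Size of a baseline gap at the trigger.** Take 24 BBT and 25 MBT participants (protocol, Study Design) and assume all have a working memory score. The two-sided 10% critical value of t on 47 df is 1.678. The gap is 1.678 × √(1/24 + 1/25) = 1.678 × 0.2858 = 0.48 SD.

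**4. What the ANOVA does with such a gap.** With two groups and two sessions, the group-by-session test compares change scores. With equal variances, no treatment effect and pre-post correlation r, an observed baseline gap of d SD gives an expected difference in change of (1 − r)d. The documents give no r; I assume 0.5 to 0.8.

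- r = 0.5: 0.5 × 0.48 = 0.24 SD
- r = 0.8: 0.2 × 0.48 = 0.10 SD

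ANCOVA removes this expected difference. It also has the smaller residual variance: relative to the change score, (1 − r²) / [2(1 − r)] = (1 + r)/2, which is 0.75 at r = 0.5 and 0.90 at r = 0.8.

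**5. Open choice of score.** The number of candidates is my assumption: 3 (conditions only) to 6 (3 conditions × accuracy or response time). For k independent tests, the chance of at least one two-sided p<.05 under no effect is 1 − 0.95^k. The last column comes from simulating 400,000 sets of equally correlated normal scores.

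| Candidates | Independent | Correlation 0.7 |
|---|---|---|
| 1 | 5% | 5% |
| 3 | 1 − 0.95³ = 14.3% | 11.0% |
| 6 | 1 − 0.95⁶ = 26.5% (0.2649) | 16.4% |

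These count results in either direction. Counting only those that favour BBT, still under independence, gives 1 − 0.975³ = 7.3% and 1 − 0.975⁶ = 14.1%, against 2.5% for one named score.

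**The case against.** A reader might infer that working memory can never be baseline-adjusted, however unequal the arms. The documents do not support that. The SAP is a past-tense report, and its trend rule is not expressly confined to the eight listed variables. Nor is baseline ignored: the repeated-measures ANOVA uses the pre-training score, and the SAP presents ANCOVA as a supporting check on the ANOVA effects. What is missing is that check and the information needed to see whether it was due.

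A reader might also infer that the score was free to be chosen, or was chosen, after seeing the data. That is not shown. The protocol ties the outcome to the parent registration, which is not among the documents and may name a score. The SAP also says the analysts were blind to group, although coded groups alone would not stop a choice of whichever score separates them.

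The percentages are open to challenge too. The documents give no count of candidate scores, and scores from one task in the same people are likely to be correlated. Condition could also enter the ANOVA as a within-subject factor with a single interaction test; the SAP does not say. Trends on other measures say little about working memory, and two of the three (CPT and mft power) come from the same vigilance task.

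All of this stands, and it limits the claim. It does not supply a score, a baseline comparison or an ANCOVA for the secondary outcome.

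**Conclusion.** The point holds as a reporting gap with a better analysis available. The only named secondary outcome has no score in the documents, no reported baseline comparison and no ANCOVA. As written it receives a change-score comparison, and the reader cannot judge whether the SAP's own trigger was met.

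If working memory had a gap just at the trigger, about 0.10 to 0.24 SD of apparent change would be expected with no effect. That assumes equal variances and r between 0.8 and 0.5. The 14% to 26% range (about 11% to 16% at correlation 0.7) is illustrative only: it rests on an assumed 3 to 6 candidates and two-sided tests. Neither figure is evidence of actual imbalance or selection. The point concerns a secondary outcome in a study the protocol describes as one of feasibility and potential efficacy, so the change is advisable but does not decide the primary result.

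**What to change.** - Make the between-arm working memory test an ANCOVA of the post-training score on the pre-training score and group, whatever the baseline p-value. Ideally apply the same rule to every outcome, including the CPT, so that the primary and secondary outcomes are not handled differently.
- Show pre-training working memory values by arm.
- If the parent registration states a score, use it and cite it. If not, report every condition and score, or one summary across ND, ID and AD, and label the choice post hoc. The SAP already reports results, so naming a score now cannot restore pre-specification.

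The cost is SAP wording and, for working memory, one ANCOVA for each score reported, on data already collected before and after training. The downside is that condition-specific effects become exploratory.
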